##### **7.1.2. Demographic and Baseline Characteristics**

The demographic characteristics including, age, sex, ethnicity, race, height at baseline, weight at baseline, BMI at baseline will be summarized with descriptive statistics. In addition, the following categories will be summarized: 18-64, 65-84 and  $\geq 85$  based on the randomized analysis set.

Listings of demographic characteristics will also be produced.

The details of the planned displays are in programming specification document.

##### **7.1.3. Protocol Deviations**

Important protocol deviations will be summarized.

Protocol deviations will be tracked by the study team throughout the conduct of the study.

The details of the planned displays are in programming specification document.

#### **7.1.4. Prior and Concomitant Medications**

Prior and concomitant medications will be coded using WHO Drug Dictionary. Concomitant medications will be summarized as number and percentage of subjects. For classifying study phase for concomitant medications, use the following definition.

Study Phase	Definition
Prior	If medication end date is not missing and is before date of first dose of study medication.
Concomitant	Any medication that is not a prior

Please refer to Section [7.2.6](#) for handling of missing and partial dates for concomitant medication.

The details of the planned displays are in programming specification document.

#### **7.1.5. Study Intervention Exposure and Compliance**

A summary of Overall cumulative exposure to HB-adMSCs will be produced.

The details of the planned displays are in programming specification document.

### **7.2. Appendix 2 Data Derivation Rule**

#### **7.2.1. Criteria for Potential Clinical Importance**

The potential clinical importance criteria are not defined this trial. A laboratory value that is outside the reference range is considered either high abnormal or low abnormal will be displayed based on lab normal range data.

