- Incidence and risk of AEs of special interest (serious or nonserious), including thromboembolic events, peripheral events defined as, thromboembolism of the extremities, also infections and hypersensitivities.
- Clinically significant changes in laboratory values, vital signs, weight, and physical examination results.

Secondary Endpoints

The safety and efficacy endpoints of this study will be evaluated by identifying changes from Baseline to Week 52 in the following:

- Expanded Disability Status Scale (EDSS)
- The Barthel Index
- 9-Hole Peg Test
- Patient Health Questionnaire (PHQ-9)
- Incidence of treatment-emergent Adverse Event (TEAEs) and serious Adverse Events (SAEs).
- Incidence and risk of AEs of special interest (serious or nonserious), including thromboembolic events, peripheral events defined as, thromboembolism of the extremities, also infections and hypersensitivities.

- Clinically significant changes in laboratory values, vital signs, weight, physical examination results and Multiple Sclerosis concomitant medications.

Investigational Plan.

[figure not shown]
This is a randomized, double-blind, single center, phase 2 study to assess efficacy and safety of multiple HB-adMSCs vs. Placebo for the treatment of Multiple Sclerosis. The trial includes a screening period of up to 4 weeks, a 32-week treatment period, and a safety Follow-up period of 20 weeks after the last investigational product administration.

This clinical trial will be opened to enroll 24 eligible participants diagnosed with Multiple Sclerosis. Patients' recruitment will be conducted by the study team, if eligible participants are identified based on eligibility criteria, a screening visit will be scheduled. Informed consent form will be given to the study participants and signed before any study procedures. Informed consent form will include information about the clinical trial and some aspects should be considered during this process.

- Principal investigator and/or study team will make sure the participant was alert, and able to read and understand the language in the consent form.
- Principal investigator and/or study team will make sure the participant takes ample time to carefully read the consent form.
- Principal investigator and/or study team will make sure the consent form is carefully explained to the participant and any questions or concerns are addressed before signing the form.

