7. Visually confirm temperature tape is in biohazard bag and is within range (2° - 8° C), document compliance.
8. Visually confirm syringe is closed with cap.
9. Remove syringe from bag and begin mixing syringe, gently rocking back and as well as rolling between hands, bringing the study treatment to room temp, and suspending them into a homogenous solution. No particulates should be visible.
10. Inject the contents into a 250cc bag of normal saline for injection
11. Properly label the infusion bag with the subject ID, D.O.B, preparation date, time and expiration and cover it with an amber bag.

Once, the study treatment has been mixed by the unblinded pharmacist following the above procedures, the infusion nurse or designated study staff will administer the study treatment as follows:

1. Confirm that the subject number and DOB placed on the amber bag label belong to the subject receiving the infusion.
2. Administer the infusion solution over a period of 1h (infusion rate 4-5ml/min).
3. Do not store or reuse any unused portion of the infusion solution. Any unused product or waste material should be disposed in a biohazard container.
4. Complete the source documents of the visit to accurately collect the start and end times of the infusion and add comments if necessary.
5. The study's subject will be monitored for a total of 2 hours from drug exposure to discharge.
 - During the Investigational product administration (1 hour) vital signs will be measured at minute 0, 15, 30, 45, and 60.
 - Post infusion, vital signs will be measured at minute 90 and 120.
6. Follow study procedures as described in the schedule of assessments of the visit.

Investigational Product Assignment (Randomization and Blinding)

A total of 24 eligible subjects will be randomized to either placebo (approx. 12) or active drug (approx. 12) (HB-adMSCs) in a 1:1 balanced design. The randomization will be applicable only to eligible subjects. If a subject is not eligible during the screening process for study participation, this subject shall not be randomized to any group.

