A repeat measure mixed model will be used to assess within-subject changes from baseline. correction for multiple comparisons will be employed for post-hoc comparisons. Multiple Sclerosis's assessment scores (i.e., MSQOL) at screening and infusion 1 (before treatment) will be averaged and treated as a baseline. Averaging is performed to minimize sources of variance (i.e., patient condition, assessors) and particularly to establish a reliable baseline from which to establish changes.

Data Handling

Case Report Forms (CRF)

As used in this protocol, the term CRF should be understood to refer to either a paper form or an electronic data record or both. Reports received by the site, or from the central laboratory should be printed, retained as source documentation, and signed by the principal investigator, indicating which values are considered clinically significant and to be reported as AEs if applicable.

The completion, review, and approval of all CRFs, as well as the completeness and authenticity of all clinical and laboratory data entered on these CRFs, are always the PI's personal responsibility. Signature of Principal Investigator will be required to attest that the information contained on the CRFs is accurate.

Original CRFs should not be made available in any form to third parties, except for authorized representatives of Hope Biosciences Stem Cell Research Foundation or appropriate regulatory authorities, without written permission from Hope Biosciences Stem Cell Research Foundation.

Changes in the Conduct of the Clinical Trial

Protocol Amendments

Any change to the protocol will need to have a protocol amendment submitted to the IND, and FDA and IRB must agree prior to proceeding.

Premature Clinical Trial Termination

Both the Study Investigator and Sponsor have the right to terminate the clinical trial at any time. Should this become necessary, the procedures will be agreed upon after consultation between the two parties. In terminating the clinical trial, the Sponsor and the Study Investigator will ensure that adequate consideration is given to the protection of the best interests of the study participants. Regulatory authorities and IRB will be informed.

In addition, the Sponsor reserves the right to terminate the participation of any clinical trial site. Conditions that may warrant termination include, but are not limited to:

- Insufficient adherence to protocol requirements
- Failure to enter patients at an acceptable rate

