

• To identify the safety of intravenous infusions of HB-adMSCs vs. Placebo in patients with Multiple Sclerosis as determined by changes in Patient Health Questionnaire (PHQ-9) (Time frame: Baseline to Week 52).

• To assess the safety of intravenous infusions of HB-adMSCs vs. Placebo in patients with Multiple Sclerosis as determined by the incidence of adverse events or serious adverse events (Time frame: Baseline to Week 52).

	

• Change from baseline at Week 52 in Patient Health Questionnaire (PHQ-9) scores following treatment with HB-adMSCs or Placebo

• Incidence of treatment-emergent Adverse Event (TEAEs) and serious Adverse Events (SAEs)

• Incidence and risk of AEs of special interest (serious or nonserious), including thromboembolic events, peripheral events defined as, thromboembolism of the extremities, also infections and hypersensitivities.

• Clinically significant changes in laboratory values, vital signs, weight, physical examination results and Multiple Sclerosis concomitant medications.

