#### **5.3.2.3. Clinical Laboratory data**

Laboratory evaluations will include the analyses of Biochemistry laboratory tests, Hematology laboratory tests and Urinalysis. The details of the planned displays are in programming specification document.

All laboratory parameters, including numerical urine analysis parameters will be summarized descriptively. Categorical urine analysis results will be summarized using count and percentage based on subjects.

Results of urine pregnancy test will be listed in individual subject data listings only.

Individual laboratory evaluations will be listed. In addition, a listing containing individual subject laboratory values outside the normal reference ranges will be provided.

Data recorded at unscheduled assessments will not be included in tables and figures but will be listed.

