#### **5.3.3. Additional Safety Assessments**

The analyses of non-laboratory safety test results will include physical examination and vital signs.

Physical Examination and Vital signs will be summarized using count and percentage based on subjects. The vital signs based on visit and change from baseline will be summarized using descriptive statistics.

Individual Vital signs, Physical Examination evaluations will be listed.

The details of the planned displays are in programming specification document.

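### The SAP neither defines the endpoint of clinically significant changes in laboratory values, vital signs, weight and examination nor specifies a by-arm count of it, and infusion-time vital signs have no within-infusion analysis

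*SAP*

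**What the plan says.** The protocol lists the endpoint under Primary Endpoints as "Clinically significant changes in laboratory values, vital signs, weight, and physical examination results" and repeats it, with MS medications added, under Secondary Endpoints. SAP 2.1 carries it as secondary only: "Clinically significant changes in laboratory values, vital signs, weight, physical examination results and Multiple Sclerosis concomitant medications". Neither document states the metric (patients, events or mean change).

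On the criterion, SAP 7.2.1 states "The potential clinical importance criteria are not defined this trial" and offers high and low flags against the laboratory's reference range instead.

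The planned displays are:

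- **Laboratory (SAP 5.3.2.3).** "All laboratory parameters, including numerical urine analysis parameters will be summarized descriptively", and "a listing containing individual subject laboratory values outside the normal reference ranges will be provided". Unscheduled results are listed but kept out of tables and figures.
- **Vital signs and examination (SAP 5.3.3).** Numbers and percentages of patients, without saying what is counted, and then "The vital signs based on visit and change from baseline will be summarized using descriptive statistics".
- **Adverse events (SAP 5.3.2.2).** Treatment-emergent events are tabulated by patients and by events. The window runs from the first infusion to the Week 42 visit or early withdrawal, and later events are listed.

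The protocol does have a criterion: the investigator's judgement. Under Vital Signs and Physical Examinations the investigator rates abnormal findings, and significant ones become adverse events. Under Case Report Forms the investigator signs laboratory reports, "indicating which values are considered clinically significant and to be reported as AEs if applicable". The administration instructions say that during each infusion "vital signs will be measured at minute 0, 15, 30, 45, and 60", with two further readings at minutes 90 and 120.

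**The concern.** A stated endpoint should be traceable from its definition to a named analysis. Here the definition sits with the investigator under the protocol, and the SAP does not pick it up. Means by visit, out-of-range listings and counts of unstated categories do not answer how many patients in each arm had a clinically significant change, or in which domain.

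The vital-sign design raises a second question. The product is given intravenously six times, and dense readings are taken around each infusion. The SAP compares vital signs with the study baseline only. At Infusions 2 to 6 that baseline is a reading taken 4 to 32 weeks earlier, not the one taken just before the infusion. The SAP also does not say which of the same-day readings stands for the visit, so two programmers could produce different summaries from the same data.

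What is at stake is the reporting of a safety endpoint in a small trial of a cell product, and measured changes that are not written up as adverse events.

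**Working it through.** The plan states no figure for this endpoint, so there is none to reproduce. The check sets the documents side by side and then sizes the gap.

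**1. Endpoint against planned analysis**

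| Domain | Who rates significance (protocol) | What the SAP tabulates |
|---|---|---|
| Laboratory | Investigator, on signed reports | Descriptive statistics; out-of-range values listed; unscheduled results listed only |
| Vital signs | Investigator | Patient counts of unstated categories; values and change by visit |
| Examination | Investigator | Patient counts of unstated categories |
| Weight | Within the examination section | Named only as a baseline characteristic (7.1.2); after baseline only the general rule for continuous data in 5.1.1 could reach it |

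No row contains a by-arm count of patients with a significant change.

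**2. The adverse-event route**

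- Safety laboratory visits are Visits 1, 2, 6 and 9, so the scheduled post-baseline draws are at Weeks 24 and 52.
- The treatment-emergent window ends at Week 42. One of the 2 scheduled post-baseline draws therefore falls outside it. An event with onset first recorded at Week 52 would be listed and not summarised, unless it is serious.
- Clearly related abnormal results are grouped under one diagnosis (Recording of Adverse Events), so the domain cannot always be recovered from the event term.
- The Y and N definitions of treatment-emergent in SAP 7.2.2 are the reverse of 5.3.2.2. That is a separate error, but this route depends on it.

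**3. Infusion-time vital signs**

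- Readings per infusion: 5 (minutes 0, 15, 30, 45, 60) + 2 (minutes 90, 120) = 7.
- Per fully dosed patient: 7 × 6 infusions = 42. In 24 patients: 42 × 24 = 1,008.
- Minute-0 readings: 1 × 6 × 24 = 144.
- After minute 0: 6 × 6 = 36 per patient, and 36 × 24 = 864 = 1,008 − 144.

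No SAP section specifies an analysis of these 864 sets against their own minute 0. The rule for repeated same-day measurements (7.2.5) covers laboratory tests only. The protocol itself refers to a fall from the pre-infusion level under Infusion Stopping Rules, so it treats change within an infusion as informative.

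**4. Why an out-of-range listing is not the endpoint**

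- Listed analytes: 19 (metabolic panel) + 19 (blood count) + 3 (coagulation) = 41.
- Post-baseline results: 41 × 2 visits = 82 per patient, and 82 × 12 = 984 per arm.
- The documents give no rate for chance out-of-range results. Assuming 1% to 5% per result, the expected number per arm is 984 × 0.01 = 9.8 to 984 × 0.05 = 49.2. Correlation between analytes does not change an expected count.

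So some 10 to 49 flags per arm could arise by chance, with nothing to separate them from significant changes.

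**5. What a by-arm count could show with 12 per arm**

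- 0 of 12: exact two-sided 95% upper limit = 1 − 0.025^(1/12) = 26.5%.
- Fisher's exact test, two-sided: 4 v 0 gives p = 0.093; 5 v 0 gives p = 0.037.

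The table would describe, not test.

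**The case against.** The best defence is that the endpoint is already covered. The protocol makes an abnormal result an adverse event when the investigator considers it clinically significant, and it says so again for vital signs and examination findings. The SAP then tabulates such events by patient, system organ class and preferred term. SAP 5.3.3 also plans patient counts for vital signs and examination. Potential clinical importance in 7.2.1 is a programmed-threshold idea and is not the same as the investigator's clinical significance. Display details are in a programming specification that is not available here.

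Much of this stands, and it rules out several stronger readings:

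- A reader might infer that the endpoint is never counted by arm, or that only visit means and listings are planned. The adverse-event tables and the counts in 5.3.3 contradict that.
- A reader might infer that a between-arm difference in infusion reactions would appear in no table. Recognised reactions are adverse events. Hypersensitivities and thromboembolic events have a special-interest table, and events are sought at each infusion visit and in the 24-hour call.
- A reader might infer that the infusion readings are averaged away. No section averages them; the SAP is silent.
- A reader might infer that SAP 5.3.2.3 and 7.2.4 flatly contradict each other on unscheduled samples. Both keep them out of by-visit summaries. The worst-value clause in 7.2.4 simply has no laboratory table to act on.

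The defence does not close the gap. The adverse-event route stops at Week 42 for an endpoint that runs to Week 52, and it mixes domains. The wording on signed laboratory reports sends values to adverse events only where applicable. The counts in 5.3.3 have no stated content. A programming specification can hold table layouts, but an endpoint's definition belongs in the SAP.

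**Conclusion.** The concern holds in a limited form. The plan has a usable criterion in the investigator's rating, but the SAP does not adopt it and names no by-arm table for the endpoint. What reaches the tables does so through adverse events up to Week 42 or through undefined counts. Weight has no post-baseline analysis of its own, unscheduled laboratory results are excluded from tables, and 36 post-minute-0 vital-sign sets per fully dosed patient (864 in 24) have no within-infusion analysis.

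The 864 assumes that all 24 patients receive all six infusions. It measures unanalysed data, not the size of any bias. Reading the endpoint as a count of patients is an inference, since neither document states the metric. The verdict also assumes that the unseen programming specification does not supply the definition. The gap affects the completeness of safety reporting and should be corrected before unblinding; it does not touch the efficacy analysis.

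**What to change.** Replace SAP 7.2.1 and extend 5.3.2.3 and 5.3.3 as follows:

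- **(a) Endpoint table.** Define the endpoint as the investigator's recorded rating of clinical significance. Tabulate, by arm and by domain (laboratory, vital signs, weight, examination), the patients with at least one such finding through Week 52 that was not present at baseline, with exact 95% confidence intervals. Label it descriptive.
- **(b) Laboratory shift table.** Show, by arm, the shift from baseline to the worst post-baseline category, including unscheduled samples. Amend 5.3.2.3 so that its exclusion applies to by-visit summaries only, in line with 7.2.4.
- **(c) Vital signs.** State which reading represents a visit. Summarise, by arm and infusion, the change from that infusion's minute 0 to the most extreme value through minute 120.

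Do not add a count of patients meeting the infusion-stopping values yet. The protocol's hypotension wording gives a range of 30-40 without naming the pressure component, and the sponsor must reconcile it first. Correct the reversed definitions in 7.2.2 at the same time.

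The cost is a few extra tables. The readings are already scheduled. The significance ratings may need data entry if they exist only on signed paper reports, because the documents show no database field for them.

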#### **7.2.2. Study Period**

Adverse events will be classified according to the time of occurrence relative to the study intervention period.

Treatment emergent	Definition
Y	If event start date is not missing and is before date of first dose of study medication.
N	Any event started on or after date of first dose of study medication or event date is missing or partial

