Laboratory Samples.	
Screening, Week 0, 24 and 52.
 
Screening
 
Week 0 – Infusion 1
 
Week 4 – Infusion 2
 
Week 8 – Infusion 3
 
Week 16 – Infusion 4
 
Week 24 – Infusion 5
 
Week 32 – Infusion 6

Visits by Weeks	

Week 42 – Follow Up.

Week 52 – End of Study

“A Randomized, Double-Blind, Single Center, Phase 2, Efficacy and Safety Study of autologous HB-adMSCs vs Placebo for the Treatment of Patients with Multiple Sclerosis”

Objectives

Primary Objective

- To investigate the efficacy of intravenous infusions of HB-adMSCs vs Placebo in patients with Multiple Sclerosis as determined by improvements in Multiple Sclerosis Quality of Life (MSQOL)-54 Instrument. (Time frame: Baseline to Week 52).

Secondary Objectives

- To evaluate the efficacy of intravenous infusions of HB-adMSCs vs. Placebo in patients with Multiple Sclerosis as determined by changes in Expanded Disability Status Scale (EDSS) (Time frame: Baseline to Week 52).
- To assess the efficacy of intravenous infusions of HB-adMSCs vs. Placebo in patients with Multiple Sclerosis as determined by changes in The Barthel Index (Time frame: Baseline to Week 52).
- To determine the efficacy of intravenous infusions of HB-adMSCs vs. Placebo in patients with Multiple Sclerosis as determined by changes in 9-Hole Peg Test (Time frame: Baseline to Week 52).
- To identify the safety of intravenous infusions of HB-adMSCs vs. Placebo in patients with Multiple Sclerosis as determined by changes in Patient Health Questionnaire (PHQ-9) (Time frame: Baseline to Week 52).
- To assess the safety of intravenous infusions of HB-adMSCs vs. Placebo in patients with Multiple Sclerosis as determined by the incidence of adverse events or serious adverse events (Time frame: Baseline to Week 52).

Endpoints

Primary Endpoints

The safety and efficacy endpoints of this study will be evaluated by assessing changes from Baseline to Weeks 52 in the following:

- Multiple Sclerosis Quality of Life (MSQOL)-54 Instrument. This 54-item questionnaire provides 12 subscales, two summary scores, and two extra single-item measures. The subscales are physical function, role limits-physical, emotional role restrictions, pain, emotional well-being, energy, health perceptions, social function, cognitive function, health distress, overall quality of life, and sexual function.
- Incidence of treatment-emergent Adverse Event (TEAEs) and serious Adverse Events (SAEs).

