### **5.3.2.2. Adverse Events**

AEs will be coded using the most recent version of the Medical Dictionary for Regulatory Activities (MedDRA).

A treatment emergent adverse event (TEAE) is defined as an event that has onset date on or after the first day of exposure to infusion treatment and on or before the first safety follow up at week 42/early withdrawal date. Here the first day of exposure is defined as the first day of exposure to infusion treatment.

Treatment emergent Adverse events TEAEs are summarized descriptively, whereas non-TEAEs are presented in listings. TEAE data will be displayed in terms of the number of subjects with at least one event (N), percentage of subjects with at least one event (%) and the number of events (E).

Summaries of TEAEs and of serious AEs will be presented as an overview including all AEs, serious AEs, AEs by severity, AEs by relation to treatment, action to AEs and treatment advised, and outcome of AEs.

Furthermore, summary tables based on system organ class and preferred terms are made for:

- All TEAEs
- Serious AEs
- AEs leading to withdrawal of study
- Incidence and risk of AEs of special interest (serious or nonserious), including thromboembolic events, peripheral events defined as, thromboembolism of the extremities, also infections and hypersensitivities.

Individual adverse events will be listed.

The details of the planned displays are in programming specification document.

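### SAP 7.2.2 reverses the treatment-emergent flag (before first dose = Y, on or after = N) and contradicts the TEAE definition in SAP 5.3.2.2

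*SAP*

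**What the plan says.** SAP 7.2.2 (Study Period) is the derivation rule for the treatment-emergent flag. Its Y row reads "If event start date is not missing and is before date of first dose of study medication". Its N row reads "Any event started on or after date of first dose of study medication or event date is missing or partial". It sets no end to the window.

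SAP 5.3.2.2 (Adverse Events) defines a TEAE by a window with a start and an end. The start is worded "has onset date on or after the first day of exposure to infusion treatment". For the end, the section uses the limit "on or before the first safety follow up at week 42/early withdrawal date". It then says how the flag is used: "TEAEs are summarized descriptively, whereas non-TEAEs are presented in listings".

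The protocol introduces its primary endpoints with "The safety and efficacy endpoints of this study will be evaluated by assessing changes from Baseline to Weeks 52 in the following", and the list includes "Incidence of treatment-emergent Adverse Event (TEAEs) and serious Adverse Events (SAEs". The secondary endpoints open with "The safety and efficacy endpoints of this study will be evaluated by identifying changes from Baseline to Week 52 in the following" and repeat the same item. SAP 2.1 carries it as a secondary endpoint. SAP 5.4 declares no departure from the protocol's analyses.

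SAP 7.2.6 imputes adverse event start dates that lack the day, or the day and month. It leaves completely missing start dates as they are.

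**The concern.** The two sections give opposite answers for every fully dated event up to Week 42, and the SAP does not say which one prevails. Section 7.2.2 sits in the data derivation appendix, where a programmer would look for the flag. TEAE tables built from it would compare the arms on pre-dose events alone, and events after infusion would drop out of them. TEAE incidence is a named protocol endpoint, so this is more than a matter of presentation.

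Two related points have to be settled in the same edit, because swapping the labels alone would not make the sections agree:

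- **Window end.** Section 5.3.2.2 stops at Week 42 or early withdrawal, and 7.2.2 does not stop. The protocol's time frame runs to Week 52, and Visit 9 collects adverse events.
- **Partial and missing dates.** Section 7.2.2 treats these as a class of their own. It does not say how that fits with the imputation in 7.2.6.

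**Working it through.** There is no plan figure to reproduce, because the issue is a classification rule. I applied both rules, and 7.2.2 with its labels swapped, to the same hypothetical onset times.

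| Onset | 5.3.2.2 | 7.2.2 as printed | 7.2.2 with labels swapped |
|---|---|---|---|
| 14 days before first dose | N | Y | N |
| Day of first dose | Y | N | Y |
| Week 4 | Y | N | Y |
| Week 24 | Y | N | Y |
| Week 32 + 1 day | Y | N | Y |
| Week 42 | Y | N | Y |
| Week 48 | N | N | Y |
| Partial date | depends on the imputed date | N (by the partial-date clause) | Y |
| Missing date | cannot be met | N | Y |

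As printed, 7.2.2 disagrees with 5.3.2.2 on every fully dated row through Week 42. Swapping the labels removes those conflicts, but leaves differences after Week 42 and for partial or missing dates.

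**Size, as time.** The inputs are a screening period of up to 4 weeks and a last visit at Week 52 (Protocol, Investigational Plan), and the Week 42 limit in SAP 5.3.2.2. The protocol's adverse event reporting period starts with the first study procedure and ends about 20 weeks after the last infusion: 32 + 20 = Week 52.

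- With 4 weeks of screening, the total is 4 + 52 = 56 weeks.
  - Y under 5.3.2.2, N under 7.2.2: 42/56 = 75.0%.
  - N under 5.3.2.2, Y under 7.2.2: 4/56 = 7.1%.
  - N under both: (52 − 42)/56 = 10/56 = 17.9%.
  - Total reclassified: (42 + 4)/56 = 46/56 = 82.1%.
- With no screening time, the total is 52 weeks: 42/52 = 80.8%, 0/52 = 0% and 10/52 = 19.2% respectively.

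**Partial dates.** Suppose the first dose is on 15 March and the event start is recorded as February with the day missing. Before imputation, the partial-date clause in 7.2.2 gives N. The entry is also not wholly missing and is clearly before first dose, so it can be read as fitting the Y row as well; the rows overlap. Section 7.2.6 sets the date to 1 February, and 7.2.2 as printed then gives Y. If the day is missing and the month is March, 7.2.6 sets onset to the first-dose date unless a full stop date falls before it. That event is a TEAE under 5.3.2.2 and N under 7.2.2 as printed.

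**The case against.** The strongest reply is that this is a clerical slip with a usable rule elsewhere. The definition in 5.3.2.2 is in the main text and its start rule is sound. The Y row of 7.2.2 is almost the same sentence as the prior-medication rule in SAP 7.1.4, which suggests a template carried over. The SAP refers display details to a programming specification that is not among the documents, so we do not know which rule would be programmed. Table 4 schedules adverse event assessment only from Visit 2, and conditions found at screening go to medical history. Tables built from 7.2.2 would therefore be nearly empty and someone might notice. All of that stands. It makes the harm conditional, but it does not make the written rule right.

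Three narrower points also stand in part:

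- The serious, withdrawal and special-interest tables are not expressly limited to TEAEs and may be unaffected. Individual events are listed in any case.
- As printed, Weeks 42 to 52 are N in both sections, so that conflict appears only once the labels are corrected. The protocol does not define a treatment-emergent window of its own, so a shorter one is possible. It should be declared, since SAP 5.4 reports no change.
- Section 7.2.2 does assign missing dates, to N as printed. Swapping the labels would turn that into Y, whereas 5.3.2.2 cannot be met without an onset date. One stated rule is still needed.

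**Conclusion.** The concern holds and must be fixed. SAP 7.2.2 as printed is the reverse of the TEAE definition in SAP 5.3.2.2, and following it would give a wrong result for a protocol endpoint. If the tables were programmed from 7.2.2, the 42 weeks from first dose to Week 42 would move out of the TEAE summaries. That is 75% to 81% of the reporting period for screening of 4 to 0 weeks. The screening weeks, 7% to 0%, would move in. The remaining 18% to 19% is N under both rules.

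These are shares of calendar time for a subject followed to Week 52, not shares of events; the documents give no event rate. The consequence assumes that programming follows 7.2.2. The contradiction itself needs no assumption.

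**What to change.** Correct the labels and put the same definition in 7.2.2 and 5.3.2.2, for example:

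> Y: onset, after imputation of partial dates under 7.2.6, on or after the date of first dose and on or before [window end].
> N: onset, after the same imputation, before the date of first dose or after [window end].

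Use one window end in both sections. There are two options:

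1. The Week 52 visit, or last study contact for early withdrawals. This matches the protocol's Baseline to Week 52 time frame and needs no declared change.
2. The present Week 42 or early-withdrawal limit, declared in SAP 5.4 as a change from the protocol.

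Add to both sections one rule for a completely missing start date, since 7.2.6 does not impute it. A workable rule, which is my proposal and not taken from the documents, is Y unless the end date is before the first dose.

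The cost is wording in 7.2.2 and 5.3.2.2 (and 5.4 under option 2) and one corrected derivation, made before unblinding. No new data are needed.
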